7.3. Definition of DLT

Toxicity will be evaluated according to the NCI CTCAE, Version 5.

Nonhematologic TEAEs of NCI CTCAE Grade ≥ 3 clearly unrelated to the underlying disease and occurring during the first cycle will be considered DLTs with the following exceptions:

- Asymptomatic laboratory changes (other than renal and hepatic laboratory values and Grade 4 lipase/amylase) that can be supplemented (reversion of Grade 4 events to Grade ≤ 2 , reversion of Grade 3 events to Grade ≤ 1 or baseline) within 72h.
- Grade 3 nausea/vomiting that can be managed subsequently with anti-emetics (Grade 3 nausea or vomiting that persists beyond 48h with or without appropriately medical intervention will be considered a DLT).
- Grade 3 fatigue lasting for <72 hours.
- Grade 3 elevation of ALT or AST that resolves to Grade ≤ 1 or baseline) within 7 days.

The following hematologic TEAEs of Grade ≥ 3 clearly unrelated to the underlying disease and occurring during the first cycle will be considered DLTs:

- Grade ≥ 3 hemolysis.
- Grade 4 neutropenia lasting more than 7 consecutive days.

- Grade 4 thrombocytopenia of any duration.
- Grade 3 thrombocytopenia with clinically significant bleeding.
- Any other Grade ≥ 4 hematologic toxicity with the following exception: Grade 4 lymphopenia

An incomplete recovery from treatment-related toxicity causing a >3 -week delay in the next scheduled infusion before the initiation of Cycle 2 will be considered a DLT.

For the purpose of dose escalation, DLTs are those events meeting the criteria above that occur before Cycle 2 Day 1 administration. Related TEAEs meeting DLT definitions occurring in later cycles or in Phase 2 (DLT-like events) will determine the suitability of the MTD dose for future studies.

Dose modifications for toxicity are described in Section 7.5.

Intrapatient dose escalation will be permitted only when patients in the next dose level cohort have completed assessments for Cycle 1 and a decision has been made that this dose level does not exceed the MTD. Eligible patients for intrapatient escalation can also be changed to a different schedule if the conditions described above are met (for example a Dose Level 1 patient could be moved to the last cleared dose level).

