7. ECOG PS 0-2
8. Age ≥ 18
9. Adequate organ function, including bone marrow, renal, hepatic, pulmonary, and cardiac function based on the last assessment performed within the Screening Period, defined as:
 - a. Absolute neutrophil count (ANC) $\geq 1,000/\mu\text{L}$;
 - b. Platelet count $\geq 50,000/\mu\text{L}$, ($\geq 30,000/\mu\text{L}$ if bone marrow plasma cells are $\geq 50\%$ of cellularity);
 - c. Hemoglobin $\geq 7.5\text{g/dL}$;
 - d. Creatinine clearance ≥ 60 mL/min (assessed as glomerular filtration rate using the Cockcroft-Gault formula);

- e. Alanine aminotransferase or aspartate aminotransferase $\leq 2.5 \times$ upper limit of normal (ULN);
- f. Total bilirubin $\leq 1.5 \times$ ULN (except for patients with Gilbert's syndrome confirmed by UGT1A1 mutation);
- g. Left ventricular ejection fraction $\geq 50\%$ as assessed by echocardiography or multi-gated acquisition (MUGA) scan; and
- h. Must have a minimum level of pulmonary reserve defined as Grade <2 dyspnea and pulse oxygenation $\geq 92\%$ on room air;

10. Prior to first dose of study drug, a woman must be either:

- Not of childbearing potential: premenarchal; postmenopausal (>45 years of age with amenorrhea for at least 12 months or any age with amenorrhea for at least 6 months and a serum follicle stimulating hormone level >40 IU/L or mIU/mL); permanently sterilized (eg, bilateral tubal occlusion [which includes tubal ligation procedures as consistent with local regulations], hysterectomy, bilateral salpingectomy, bilateral oophorectomy); or otherwise be incapable of pregnancy
- Of childbearing potential and practicing 2 highly effective method of birth control at time of informed consent and will continue through study and for at least one month after final dose of study drug. Must be consistent with local regulations regarding the use of birth control methods for subjects participating in clinical studies: e.g., established use of oral, injected or implanted hormonal methods of contraception; placement of an intrauterine device or intrauterine system; barrier methods: condom with spermicidal foam/gel/film/cream/suppository or occlusive cap (diaphragm or cervical/vault caps) with spermicidal foam/gel/film/cream/suppository; male partner sterilization (the vasectomized partner should be the sole partner for that subject); true abstinence (when this is in line with the preferred and usual lifestyle of the subject)

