7.4. Dose Escalation for ATRA and Study Stopping Rules

The phase 1b portion of the study will follow a 3+3 dose escalation design to evaluate Dose Level 1 (35.5 mg/m²/day) followed by Dose Level 2 (45 mg/m²/day) of ATRA in combination with Dara + Pom + dex for DLTs and to determine the MTD for further assessment in phase 2.

Patients will be enrolled in cohorts of 3 and assessed for DLTs over a 28-day period. In each dose level, the second and third patients can be dosed concurrently once the first patient in the cohort has gone uneventfully through the Day 8 visit. If it is necessary to enroll more than 3 patients in a cohort, and there have not been any TEAEs in the previously dosed patients in that cohort, these new patients can be enrolled concurrently.

If none of the patients in a cohort of 3 patients exhibits a DLT during the 28-day cycle, then the dose may be escalated for the next cohort of 3 patients. If 1 patient in a cohort of 3 patients exhibits a DLT, then that cohort will be expanded to a total of 6 patients. If 2 or more patients in a cohort of 3 patients exhibit a DLT, then that cohort will be deemed to have exceeded the MTD, and dose escalation will be stopped.

If the dose cohort below that at which the MTD is exceeded has enrolled only 3 patients, then 3 additional patients will be enrolled at that dose level. The MTD is defined as the highest dose with a cohort of 6 patients having no more than 1 patient with a DLT. For the cohort expansion, 3 patients will only be enrolled sequentially if a DLT observed in the initial cohort was life-threatening, it appeared before the Day 8 visit and/or the clinical team consider that based on the observed toxicity is prudent to stagger the enrollment. Sequential enrollment is not required in case of de-escalation or if no DLT was observed in the first 3 patients in a cohort.

During phase 1b dose escalation, patients who miss one or more scheduled Cycle 1 doses of ATRA for reasons other than a DLT will be replaced.

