In patients who develop reactivation of HBV while on study treatment, suspend treatment with study treatment and any concomitant steroids, chemotherapy, and institute appropriate treatment.

Resumption of study treatment in patients whose HBV reactivation is adequately controlled should be discussed with physicians with expertise in managing HBV

Daratumumab Dose Modification

Individual dose modification of daratumumab is not permitted, but dose delay is recommended as the primary method for managing daratumumab-related toxicities, as described in Section 7.5.

Daratumumab-related Toxicity Management

Refer to Section 7.5 for details on management of daratumumab injection-related reactions.

If any of the following criteria are met and the toxicity is more than expected for pomalidomide or underlying multiple myeloma, daratumumab injection must be held to allow for recovery from toxicity. If attribution is unclear, then daratumumab should be held until recovery from toxicity as noted below.

The criteria for a dose delay are:

- Grade 4 hematologic toxicity, except for Grade 4 lymphopenia
- Grade 3 thrombocytopenia with bleeding
- Febrile neutropenia
- Grade 4 Neutropenia with infection, of any grade
- Grade 3 or higher non-hematologic toxicities with the following exceptions:
 - Grade 3 nausea that responds to antiemetic treatment within 7 days
 - Grade 3 vomiting that responds to antiemetic treatment within 7 days
 - Grade 3 diarrhea that responds to antidiarrheal treatment within 7 days
 - Grade 3 fatigue that was present at baseline or that lasts for <7 days after the last administration of daratumumab
 - Grade 3 asthenia that was present at baseline or that lasts for <7 days after the last administration of daratumumab

Administration of daratumumab may be restarted upon recovery from toxicity to Grade 2 or baseline, with the exception that Grade 2 laryngeal edema or Grade 2 bronchospasm must be fully recovered. Other than on Day 1 of a cycle, if any “within-cycle” daratumumab administration does not commence within the prespecified window of the scheduled administration date (Table 3), then the dose will be considered a missed dose. Administration may resume at the next planned dosing date.

Table 3: Daratumumab-related Toxicity Management

Daratumumab Dosing Frequency	Dose Missed	Dosing Resumption
Weekly	>3 days	Next planned weekly dosing date

Table 3: Daratumumab-related Toxicity Management

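### Section 7.3 counts a listed event as a DLT only if it is clearly not due to myeloma, so events of uncertain relation to the disease drop out of the count behind escalation, the MTD and the 40% stop

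*Combined protocol and SAP*

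**What the plan says.** Section 7.3 has two lists of Cycle 1 DLTs. Nonhematologic events of Grade 3 or higher are included when they are "clearly unrelated to the underlying disease and occurring during the first cycle will be considered DLTs with the following exceptions". The hematologic list, which contains "Grade 4 thrombocytopenia of any duration", opens with the same test: "clearly unrelated to the underlying disease and occurring during the first cycle will be considered DLTs". A third route has no disease condition: incomplete recovery from treatment-related toxicity that causes a delay of more than three weeks "in the next scheduled infusion before the initiation of Cycle 2 will be considered a DLT". Nothing in 7.3, 7.4 or section 9 says how to classify an event whose relation to the myeloma is uncertain.

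The 7.3 definition feeds three decisions:
- **Escalation (7.4):** "If 1 patient in a cohort of 3 patients exhibits a DLT, then that cohort will be expanded to a total of 6 patients"; two or more DLTs in three patients exceed the MTD.
- **The MTD (7.4):** the highest dose with no more than 1 DLT in a cohort of 6.
- **The safety stop (9.4):** the trial stops if events meeting DLT criteria exceed 40%.

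Section 10.3.1 grades causality differently. An event is Suspected when there is a reasonable possibility that study drug caused it.

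**The concern.** In a DLT definition, the handling of doubt decides which way the count errs. Here doubt about the disease removes the event. The same Cycle 1 event can be recorded as suspected to be drug-related under 10.3.1 and still not be a DLT under 7.3, because myeloma is also a possible cause.

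Such doubt is foreseeable for cytopenias. Inclusion criterion 9b lowers the platelet floor from 50,000/µL to 30,000/µL "if bone marrow plasma cells are" at least 50% of cellularity. Table 4 puts Grade 4 thrombocytopenia below 25,000/µL. A patient who enters at 30,000/µL reaches Grade 4 after a fall of just over 5,000/µL (30,000 − 25,000), with a marrow at least half replaced by plasma cells. It may be hard to call that fall clearly unrelated to the disease.

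There is a further, narrower route. Under 7.4 and 9.2, a patient who misses Cycle 1 ATRA for a reason other than a DLT is replaced. If an uncounted event causes the missed dose, the patient leaves the evaluable set as well as the DLT count. Section 4.1 and Table 1 place ATRA only on days -2, -1 and 1 of the cycle, so this applies only to events early enough to disrupt those doses.

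With cohorts of three to six, reclassifying one event can change the decision on a dose.

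**Working it through.** **The plan's own figure.** Section 9.2 gives 3 to 12 patients for phase 1b. Following every path through 7.4 with two dose levels, including enlarging the lower dose to 6 where required, gives possible totals of 3, 6, 9 and 12. The stated range is reproduced.

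**Which events are affected.**

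| Relation of a listed Cycle 1 event to myeloma | DLT under 7.3 as written? |
|---|---|
| Clearly not due to myeloma, drug cause known or unknown | Yes |
| Clearly due to myeloma | No |
| Uncertain | No, unless it meets the separate delay route, which needs a treatment-related judgement |

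Only the third row is at issue.

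**Effect on the decision rules.** Let p be the true probability that a patient has a DLT-grade event in Cycle 1, and u the share of such patients not counted because the relation to disease is uncertain. The counted rate is c = p(1 − u). The documents give neither p nor u, so both are assumed and shown as ranges. The model takes patients as independent, assumes that a patient with an uncounted event has no other counted DLT, and leaves out the replacement route.

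- Clearing a dose (0/3, or 1/3 then 0/3): (1 − c)³ + 3c(1 − c)² × (1 − c)³. Section 7.4 does not spell out the step after expansion; I take it from the limit of 1 in 6.
- Meeting the MTD rule (at most 1 in 6): (1 − c)⁶ + 6c(1 − c)⁵.

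Example at p = 0.33 and u = 20%: c = 0.264, and the MTD rule gives 0.736⁶ + 6 × 0.264 × 0.736⁵ = 0.159 + 0.342 = 0.501.

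| p | u | c | Clears dose | At most 1 in 6 |
|---|---|---|---|---|
| 0.33 | 0 | 0.330 | 0.434 | 0.358 |
| 0.33 | 20% | 0.264 | 0.570 | 0.501 |
| 0.33 | 30% | 0.231 | 0.641 | 0.580 |
| 0.33 | 50% | 0.165 | 0.783 | 0.741 |
| 0.40 | 0 | 0.400 | 0.309 | 0.233 |
| 0.40 | 20% | 0.320 | 0.454 | 0.378 |
| 0.40 | 30% | 0.280 | 0.536 | 0.464 |
| 0.40 | 50% | 0.200 | 0.709 | 0.655 |

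The last column bears on the dose taken into phase 2, because 0/3 alone does not meet the MTD definition.

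**Effect on the 40% stop.** If the true rate were 50% and a quarter of events were left out, the counted rate would be 0.50 × 0.75 = 37.5%, below the stop.

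**The case against.** **Scope.** A reader might infer that every Grade 3 or higher event of uncertain cause is lost. The text does not support that. Section 7.3 requires no attribution to ATRA or any other study drug, so toxicity of the backbone drugs and unexplained events count if they are clearly not myeloma. It follows that a net low bias for ATRA itself is not shown; what is shown is that one class of events is omitted.

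**Section 7.5.** A reader might also infer that 7.3 contradicts the daratumumab rules, which apply when "the toxicity is more than expected for pomalidomide or underlying multiple myeloma, daratumumab injection must be held to allow for recovery from toxicity" and add: "If attribution is unclear, then daratumumab should be held until recovery from toxicity as noted below". The defaults run in opposite directions, but one is a hold rule for one drug in one patient and the other defines an endpoint. The ATRA rules in 7.5 contain no such sentence. This is a contrast, not a contradiction.

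**How often doubt arises.** Time course, recovery off drug and a falling M-protein may settle the cause, so it would be too strong to say that Grade 4 thrombocytopenia in such a patient could never count. Outside the 9b exception, entry requires platelets of at least 50,000/µL. Renal events are a weak example, since creatinine clearance must be at least 60 mL/min. Section 4.2 reports Grade 3 neutropenia in 78% and thrombocytopenia in 19% on the three-drug backbone. That shows cytopenias are common but gives no DLT rate.

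**Safeguards.** The study team reviews all treated patients before escalation and documents its decisions in writing (7.4). Section 9.4 has stops for Grade 4 nonhematologic events and for fatal events. The phase 1b endpoints report Grade 3 or higher events without a disease filter, and the monitoring committee meets quarterly (11.3). These soften the effect. They do not return an uncertain event to the DLT count, and the Grade 4 stop does not reach cytopenias, the main case. The review in 7.4 gives no rule for such events, so the two sites could classify the same event differently.

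**Conclusion.** The point holds in this limited form: 7.3 as written excludes listed Cycle 1 events whose relation to myeloma is uncertain. The direction needs no numerical assumption, because leaving events out cannot raise the count.

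The size is illustrative. At an assumed true risk of 33%, the chance of meeting the MTD rule is 36%, rising to about 50%, 58% or 74% with 20%, 30% or 50% of events left out. The chance of clearing the escalation rule goes from 43% to 57%, 64% or 78%. If uncertain events turn out to be rare, the effect is small. No figure stated in the plan is overturned. The wording should be changed before cohort decisions depend on it.

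**What to change.** Reword the attribution condition in both sentences of 7.3, for the DLT tally only. Count a listed event whose relation to the underlying disease is uncertain, and leave out only events clearly attributable to that disease. Add no exclusion for other causes: 7.3 has none now, and a new one could remove events that currently count.

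Reconcile the wording with the causality definition in 10.3.1, which names pomalidomide, daratumumab and dexamethasone but not ATRA. In the written cohort review, list each event excluded as disease-related, with the reason.

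The change is not meant to alter dosing, hold or discontinuation rules. Because 7.6 refers to DLT criteria, the text should say that the revised condition governs the tally.

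The drafting cost is two sentences and a listing. The statistical cost is that some disease-related events will be counted, so a cohort may be expanded, or a tolerable dose not cleared, more often. For illustration, if the true risk is 20% and the tallied rate becomes 30% (both assumed), the chance of clearing falls from 71% to 49%, and of meeting the MTD rule from 66% to 42%. Listing the exclusions helps limit this, since events clearly due to myeloma stay out.

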4. OVERALL STUDY DESIGN

4.1. Study Design

This is a multicenter, open label study of Dara+Pom+Dex combined with ATRA in patients progressing on a Dara+Len+Dex regimen. The study is expected to enroll up-to a maximum of 42 patients (20-32 subjects previously exposed to Dara + Len + Dex; 10-22 subjects previously exposed to Dara + Pom + Dex)..

The phase 1b portion will follow a standard 3+3 dose escalation design with two dose levels and up to 12 patients. Under this design, the investigators will evaluate dose levels as follows:

- Dose level 1 - ATRA 35.5 mg/m²/day on days -2,-1 and 1 on a 28-day cycle in combination with daratumumab, pomalidomide, and dexamethasone
- Dose level 2 – ATRA 45 mg/m²/day on days -2,-1 and 1 on a 28-day cycle in combination with daratumumab, pomalidomide, and dexamethasone

During the dose-escalation phase and after the first cycle, and after the first cycle, patients who have not experienced a DLT, have not shown signs of PD, and in the opinion of the investigator would continue to benefit from treatment may receive additional cycles of treatment.

The phase 2 portion will be conducted in two stages. In the first stage, 10 patients will be accrued. A safety and efficacy analysis will be conducted 3 months after accrual of the first 10 patients. If there are 2 or fewer responses in these 10 patients, the study will be stopped due to futility. If the stopping rules for safety are met, then the study will be stopped due to toxicities. Otherwise, accrual will continue for a maximum of 42 in phase 1b and phase II combined.

During 28-day treatment cycles, patients will receive Dara 1800 mg subcutaneous (SC) at their current dose upon enrollment onto the study depending on their cycle. (If they are on cycles 1-2 then they will receive Dara 1800 mg SC days 1,8,15,22; if they are on cycles 3-6 they will receive Dara 1800 mg SC days 1 and 15; if they are on cycle 7 or beyond they will receive Dara 1800 mg SC on day 1).

Pomalidomide will be administered at the patient's currently tolerated dose (4,3, or 2 mg po daily) on days 1-21. For patients progressing on daratumumab, lenalidomide, and dexamethasone, the starting dose of pomalidomide will be 4 mg per standard of care.

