Before initiating the dosing of the next cohort or opening a new schedule, when safety data are available for all patients in the current cohort, key safety data will be reviewed and evaluated by the study team consistent of investigators who will review the safety of all treated patients and make decisions regarding dose escalation. In addition, further changes to the dose escalation scheme may be considered. All decisions will be documented in writing. Any decision to modify the dose escalation scheme in a direction that increases the already approved frequency of administration or dose escalation steps, will be communicated to institutional review boards (IRBs) and the protocol amended accordingly.

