Hyperglycemia \geq Grade 3	Decrease dose by one dose level. Treat with insulin or oral hypoglycemic agents as needed.
Acute pancreatitis	Discontinue subject from Dex treatment regimen.
Other \geq Grade 3 Dex-related adverse Events	Stop Dex dosing until the adverse event resolves to \leq Grade 2. Decrease by one dose level when Dex dosing is resumed.

^a If recovery from toxicities is prolonged beyond 14 days, then the dose of Dex will be decreased by one dose level when dose is restarted.

Table 7: Dexamethasone Dose Reduction Steps

Dose Level	≤ 75 years old	>75 years old
Starting Dose	40 mg	20 mg
Dose Level -1	20 mg	12 mg
Dose Level -2	10 mg	8 mg

ATRA will be administered in a divided dose of twice daily as an oral formulation at 35 mg/m²/day for Phase with dose escalation to 45mg/m²/day for 3 days. The dose expansion phase will be at the 45 mg/m²/day dose after safety and efficacy has been evaluated. The first administration of ATRA will be given in the morning, two days before the scheduled Dara infusion. The last administration of ATRA will be given in the evening of the day that Dara was administered (days -2, -1, and 1; day 1 is the day of Dara infusion).

ATRA-related toxicities

Subjects will be monitored for neurological symptoms and nutritional status. If Wernicke's encephalopathy is suspected, ATRA should be interrupted and parenteral thiamine should be initiated.

Pseudotumor cerebri

This complication has been mainly reported in patients aged <20 years and is characterized by presence of severe headache with nausea, vomiting, and visual disorders.

It is recommended to temporarily discontinue ATRA treatment and to administer opiates. As soon as the symptoms and the patient clinical conditions improve, the treatment with ATRA will be resumed at 50% of the previous dose during the first 7 days after the amelioration of pseudotumor cerebri. Thereafter, in absence of worsening of the previous toxicity, ATRA should be resumed at full dosage.

Table 8: ATRA Dose Reduction Steps

Dose Level	ATRA Dose reduction
Dose Level 2	45 (mg/m ²)
Dose Level 1 (Phase 1b starting dose)	35.5 (mg/m ²)
Dose Level -1	25 (mg/m ²)
Dose Level -2	20 (mg/m ²)

- ATRA will be discontinued for any Grade 4 non-hematologic toxicity.
- In the case of Grade 3 toxicity, ATRA should be held until the toxicity resolves to Grade ≤ 1 or baseline, at which time it may be resumed at a reduced dose.

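### The first laboratory exception in the DLT definition (7.3) is not monotone in severity: with baseline Grade 0–1 and Grade 2 at 72 hours, a Grade 4 peak is exempt but a Grade 3 peak is a DLT

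*Combined protocol and SAP*

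**What the plan says.** Section 7.3 makes a nonhematologic treatment-emergent event of Grade 3 or higher in Cycle 1 a DLT if it is clearly unrelated to the underlying disease and no listed exception applies. The first exception covers asymptomatic laboratory changes other than renal and hepatic values and Grade 4 lipase/amylase. The change must be one "that can be supplemented (reversion of Grade 4 events to Grade" 2 or lower, or, in the second half of the same parenthesis, "reversion of Grade 3 events to Grade" 1 or lower or baseline. Both halves have the same 72-hour window.

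Section 7.4 uses the DLT count directly. After no DLT in three patients the dose may be escalated. For a single DLT: "If 1 patient in a cohort of 3 patients exhibits a DLT, then that cohort will be expanded to a total of 6 patients". Two or more DLTs in three stop escalation. The MTD is the highest dose with at most one DLT among six patients. Section 7.4 also says that "patients who miss one or more scheduled Cycle 1 doses of ATRA for reasons other than a DLT will be replaced".

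Section 7.5 orders the two grades for ATRA dosing: "ATRA will be discontinued for any Grade 4 non-hematologic toxicity", whereas "In the case of Grade 3 toxicity, ATRA should be held until the toxicity resolves to Grade" 1 or lower or baseline, after which it may resume at a reduced dose.

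**The concern.** The more severe peak has the looser recovery target over the same window. Two patients who start at Grade 0 or 1 and are both at Grade 2 at 72 hours are classified in the wrong order: the one who reached Grade 4 is exempt, and the one who reached only Grade 3 has a DLT. A DLT rule should never become more lenient as the peak gets worse with everything else equal.

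In a 3+3 design a single patient can decide a step, so the classification matters even if such events are rare. The same definition is used beyond dose escalation. Section 7.3 lets related events of this kind in later cycles or in Phase 2 bear on whether the MTD is suitable for future studies, and 9.4 stops the trial if events meeting the DLT criteria exceed 40%.

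**Working it through.** No figure in the plan has to be reproduced; this is a classification rule. Let b be the baseline grade and g the grade at 72 hours, for a change within the scope of the exception.

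**Rule as written in 7.3**
- Grade 4 peak: exempt if g ≤ 2, otherwise a DLT.
- Grade 3 peak: exempt if g ≤ 1 or g ≤ b, otherwise a DLT.

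**All 12 combinations of b = 0–2 and g = 0–3**

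| Baseline b | Grade at 72h g | Cells | Grade 3 peak | Grade 4 peak |
|---|---|---|---|---|
| 0 or 1 | 0 or 1 | 4 | exempt | exempt |
| 0 or 1 | 2 | 2 | **DLT** | **exempt** |
| 0 or 1 | 3 | 2 | DLT | DLT |
| 2 | 0, 1 or 2 | 3 | exempt | exempt |
| 2 | 3 | 1 | DLT | DLT |

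The order is inverted in 2 of 12 cells: (b = 0, g = 2) and (b = 1, g = 2). If the baseline allowance is attached to both clauses, the Grade 4 rule becomes g ≤ 2 or g ≤ b. The table does not change, because g ≤ b adds nothing to g ≤ 2 when b is at most 2.

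**Other exceptions in 7.3.** Nausea/vomiting and fatigue are not laboratory values. ALT/AST is hepatic, so it is outside this exception. None of them exempts a Grade 3 laboratory change that is still at Grade 2 at 72 hours, and nothing in 7.4 overrides the result.

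**Effect on the 3+3 count.** By 4.1, ATRA is given "on days -2,-1 and 1 on a 28-day cycle in combination with daratumumab", and Table 1 marks no other ATRA day, so Cycle 1 ATRA is one three-day block.

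(a) Event after that block, with all Cycle 1 ATRA taken:

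| Cohort | Other DLTs | Grade 4 falling to 2 | Grade 3 staying at 2 or falling only to 2 |
|---|---|---|---|
| 3 patients | 0 | 0/3: may escalate | 1/3: expand to 6 |
| 3 patients | 1 | 1/3: expand to 6 | 2/3: stop escalation |
| 6 patients | 1 | 1/6: meets MTD definition | 2/6: does not |
| 6 patients | 0 | 0/6: meets MTD definition | 1/6: meets it (no change) |

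(b) Event that makes the patient miss a Cycle 1 ATRA dose: the exempt Grade 4 patient is replaced under 7.4 and leaves the count, while the Grade 3 patient counts as a DLT. With no other DLT this is 0/2 plus a replacement versus 1/3. Onset must fall within the three-day block, so this case is rarer still.

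The documents give no rate for such events, so these are possible consequences for a single patient, not probabilities.

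**The case against.** The strongest defence is clinical. Grade 4 to 2 and Grade 3 to 1 are both two-grade corrections, and Grade 3 to 2 is only one, so the thresholds may measure response to supplementation. The baseline allowance does not refute this: from baseline Grade 2 it exempts a one-grade fall, but it can be a separate concession that nobody must recover below the starting grade. What stands is that a two-grade idea is possible. It is not stated, and it does not remove the ordering problem: the exempt patient had the worse peak and has the same grade at 72 hours.

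A reader might infer that 7.3 contradicts 7.5. The documents do not support that. Section 7.5 governs an individual's dosing, not DLT counting. Its ATRA rules treat Grade 4 more strictly than Grade 3, but the same section restarts daratumumab at Grade 2 or baseline and resumes dexamethasone at Grade 2 or lower after other Dex-related events of Grade 3 or higher. Grade 2 is therefore an accepted recovery level in the protocol. That shows Grade 2 can be tolerable; it does not show why it should be tolerable only after the worse peak.

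A reader might also infer that the exempt Grade 4 event escapes all control, since the Grade 4 stopping rule in 9.4 leaves out asymptomatic laboratory abnormalities. That goes too far. Section 7.5 discontinues ATRA for it; 7.6 has a limited exception for life-threatening Grade 4 events, and whether this covers asymptomatic laboratory events is unclear. A value that needs supplementation is an adverse event under 10.3.5, and the Phase 1b endpoints in Section 3 include Grade 3 or higher events, dose modifications and clinically significant laboratory values. Before the next cohort it comes before investigators "who will review the safety of all treated patients and make decisions regarding dose escalation", and under 11.3 the DSMC reviews toxicities quarterly. After 0/3 the dose may, not must, be escalated.

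**Conclusion.** The point holds, as a minor one. Within the first laboratory exception of 7.3 the DLT rule is not monotone in severity in exactly two cells: baseline Grade 0 or 1, with Grade 2 at 72 hours. This rests on the literal text and does not depend on which clause the baseline allowance belongs to. The exempt Grade 4 event is acted on and reported elsewhere in the protocol; what it does not do is enter the 3+3 DLT count.

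The reach is narrow. The event must be nonhematologic, asymptomatic, correctable by supplementation, outside the excluded analytes, clearly unrelated to disease, in Cycle 1, and at exactly Grade 2 at 72 hours. Section 4.1 plans at most 12 evaluable Phase 1b patients over two dose levels. A reader might infer that the selected MTD will be too high; without event rates the documents support no such statement and no estimate of its likelihood.

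**What to change.** Reword the parenthesis in the first exception of 7.3 to: *reversion within 72h of Grade 3 events to Grade ≤1 or baseline, and of Grade 4 events to Grade ≤1 or, if baseline was Grade 2 or higher, to Grade ≤2*.

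Check of the new wording: for b = 0 or 1 and g = 2, both peaks are now DLTs; for b = 2 and g = 2, both stay exempt. Inverted cells fall from 2 of 12 to 0 of 12. No Grade 3 cell changes (0 of 12). For Grade 4 peaks over b = 0–3 and g = 0–4 (20 cells), the number reclassified depends on how the current text is read:
- If the baseline allowance attaches only to the Grade 3 clause, which is the most natural reading, 2 of 20 change: the two inverted cells.
- If it attaches to both clauses, 3 of 20 change: baseline Grade 3 with a Grade 4 peak and Grade 3 at 72 hours also becomes a DLT.

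The cost is one line of text and no extra data. The downside is that a few quickly improving Grade 4 laboratory changes become DLTs, so a dose level may be slightly harder to clear. Relaxing the Grade 3 target to Grade 2 would also remove the inversion, but by loosening the DLT rule. If a two-grade fall was intended, stating it would explain the thresholds but leave the inversion in place.
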